**Figure 2. Cumulative BNP at 1, 2, and 6 Weeks Using a Visual Analogue Scale (0 - 100)**

**Figure 3. BNP for OXTR rs53576**

Figure 2 and Figure 3 show the results of the pilot RCT. The BSM intervention group reported significantly lower BNP using a visual analogue scale (0 - 100) at 1 and 2 weeks. Participants' cumulative BNP (baseline +1 week, + 2 week, + 6 week, 0 - 400) was significantly different between groups at weeks 1, 2, and 6 (Figure 2). Higher Brief Pain Inventory interference scores at 1 week was predictive of increased BF self-efficacy scores at weeks 1, 2, and 6. Aligning with the literature BF self-efficacy scores correlated with BF exclusivity and at 6 weeks significantly predicted maternal well-being symptoms. Women experienced an **8.18 increase in BF and BNP scores over time with the minor allele A of rs53576 (Figure 3)**. The somatosensory testing results also showed that for every 1-unit increase in the Mechanical Detection Threshold test, women experienced 16.51 higher BNP scores and 4.82 higher BNP scores for the Windup Ratio. Six women with the *OXTR* rs2254298 minor allele experienced allodynia sensitivity. These risk factors will be examined in the larger study to determine replicability. The effect of the components of the BSM intervention on BNP were examined independently without significance which demonstrates the importance of a multifactorial approach. Participants' feedback of the *BSM* intervention included that texting was helpful while the paper-based daily journal was burdensome. All participants reported that the weekly survey completion was not burdensome.

algorithm and coded video recordings of a subsample of 27 infants (7 late preterm and 20 full term) jaw movements during BF. Using logistic discriminant analysis, 4 clusters of BF behaviors were identified (under preparation).

Together, the preliminary work provides evidence of the PI's ability to recruit and retain women in longitudinal studies that examine BF biobehaviors and to test the *BSM* intervention, as well as her motivation and dedication to maintaining a productive program of research. For this proposal both data collection and analysis will be facilitated by the contributions of her Co-Is. The University of Connecticut School of Nursing (UConn SON) offers a supportive environment for [name] to carry out the study, including reserved laboratory space and portable equipment. Her solid collaborations with the study sites will ensure ample enrollment of a diverse sample of women, with efficient attainment of study milestones and dissemination of findings.

### **Participant Population**

The sample size objective for the study is to recruit N = 280 women who will be randomly assigned to the *BSM* or attention control study groups at a 1:1 ratio (140 per group). The *BSM* intervention is designed for all women who initiate BF since both primiparas, and multiparas are affected (naivety or anticipatory based on prior BF experience) by some degree of pain. As it is not possible at this time to identify women at risk of early BF cessation due to pain or enhanced pain sensitivity, it is expected that the higher number of women in the *BSM* group will continue BF over the study duration.

### **Enrollment and Randomization**

After informed consent and prior to the start of data collection, the participants will be randomized to the *BSM* intervention or the attention control group and be assigned a unique participant identification number (PID#). The sample size objective for the study is to recruit N = 280 women who will be randomly assigned to the *BSM* or attention control study groups at a 1:1 ratio (140 per group). Random assignment will be performed using an established dynamic minimization algorithm, proposed by Pocock and Simon. The algorithm is implemented thru an R package called "minirand", developed by Jin et al.. The interactive tool is developed as an R shiny app embedded in REDCap. This technique will maintain the 1:1 ratio between participants assigned to the *BSM* and control conditions, but will also ensure that participant characteristics that are known to be predictive of breastfeeding outcomes will each be balanced across the study groups. Those predictive characteristics include: age, race, breastfeeding experience, expected breastfeeding duration, route of delivery, and intent to return to work.

The reason we choose this algorithm is the complexity of the randomization needed for our study. With 280 expected participants and 6 stratifying characteristics, the simple randomization may not yield a balanced arm assignment in every allocation. However, the dynamic feature of our randomization will incorporate both the existing assignments and the imbalance at each level of the stratifying characteristics and assign the next participant to minimize the overall imbalance. With the large number of total enrollments in our study, this also leads to a balanced assignment at each level of the stratifying characteristics. To retain randomness, the probability of making the "best assignment" to minimize imbalance is set to be 90%.

The randomization algorithm will be implemented in REDCap using published code that operates within "R" statistical software. An interface between REDCap and R software will be created by the project statisticians as a "Shiny app" within the RStudio development environment. The resulting R Shiny app will allow the project's recruitment staff to enter the predictive characteristics for a new participant, will compare the new participant's mix of characteristics to those of current participants, and will produce a "blinded" study group assignment for the new participant. The blinded group assignment will be presented to the recruitment staff as one of four letters: A, B, C, or D. That letter will then be entered into REDCap as the new participant's record is set-up. REDCap will be programmed to link each of the four letters to a study group (two letters for the BSM group and two others for the control group). Only the project statisticians, the project manager and the graduate assistant will know the correspondence between letters and group assignments. Four letters (and a corresponding study "arm" for each one) will be used to make it more difficult for recruitment staff to decipher which letters link to specific study groups and, therefore, to foster the likelihood that blinding to group assignment will be maintained throughout the project.

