**Justification of Sample Size:**

The sample size objective for the study is to recruit  $N = 280$  women who will be randomly assigned to the *BSM* or attention control study groups at a 1:1 ratio (140 per group). This objective provides 80% power ( $\alpha = 0.05$ , two-sided) to detect a standardized mean difference (Cohen's  $d$ ) of 0.39 or more between the *BSM* and attention control groups. It also provides 80% power to detect an odds ratio of 2.5 or more in exclusive BF between the two groups, assuming that the exclusive BF rate of the control group will be 10% higher than the national population rate in 2017 at 6, 9, 12, 18, and 24 weeks. These calculations account for "loss to follow-up" as high as 25% at 24 weeks, despite the substantially lower attrition (6%) in our pilot study. Based on our pilot study, we approached 78 women to meet our sample size of 60, with a failed screening rate of 25%. Thus, we intend to approach 374 women, which is 25% higher than our proposed study sample to meet our sample size. We anticipate that approximately 70% of the study sample will be WAHS or HHC patients.

In the pilot study, RM-ANCOVAs (with the baseline value of a measure as the covariate) revealed standardized mean differences larger than  $d = 0.39$  for the "main effect" of the intervention on BNP intensity ( $d = 0.45$ ), pain severity ( $d = 0.60$ ), cumulative pain ( $d = 0.64$ ), and BF self-efficacy ( $d = 0.48$ ) across the 1-, 2-, and 6-week time points. For BNP interference, the value of  $d$  was 0.39 at week 1, but smaller at weeks 2 and 6. Furthermore, the odds of exclusive BF in the intervention group are 2.9 times higher than the control group at 6 weeks, which is also higher than the hypothesized OR = 2.5. Therefore, we are confident that the sample size goal will be sufficiently powered to detect intervention effects on key variables for SA1 and SA2. Finally, the sample size estimate does not reflect our plans to conduct analyses based on repeated measurement of outcome variables at the 1, 2, 3, 6, 9-, 12-, 18-, and 24-week time points (due to the dearth of information regarding 24-week outcomes). Generally, the inclusion of data for an outcome variable across additional time points marginally enhances statistical power, especially for testing "main" and "interaction" effects of intervention and time.

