**For EACH Participant Population Describe Screening Procedures, if applicable**

The proposed RCT will be conducted to test the effect of the *BSM* intervention vs. an attention control group on BNP, BF exclusivity and duration, BF self-efficacy and maternal well-being to 24 weeks (Figure 4). Participants at baseline will complete assessments, quantitative sensory testing, and provide buccal cell and/or blood samples for assessment of select pain sensitivity SNPs and DNA methylation and again at 6 and 24 weeks at our research sites. At 1, 2, 3-, 9-, 12-, and 18-weeks participants will complete assessments via smartphone text and the UConn Health Research Electronic Data Capture (UConn REDCap) links, <https://health.uconn.edu/clinical-researchcenter/> when women shelter at home. If a participant does not have a smartphone, the study will provide a smartphone for them to receive texts and text links. All participants will receive educational material regarding infant development and age-appropriate play at 4, 8, 12, 16, 20, and 24 weeks to maintain contact and sustain engagement in the study. Following UConn Institutional Review Board approval, all recruitment and initial data collection will occur in collaboration with our clinical partners, at the UConn Health Center, a 234-bed tertiary care academic hospital delivering 700 infants a year with 560 women initiating BF; the Women Ambulatory Services at Hartford Hospital (HH), delivering 1000 infants a year with 800 women of diversity initiating BF (see letters of support) and women receiving private obstetric care at Hartford Hospital, delivering 2900 infants a year with 2320 initiating BF.

Prior to launch of the study, all research personnel will receive training on human subjects' research, HIPAA, and biological safety, handling and transportation. The study designated graduate assistants will develop a study binder of all protocols and each role will be established so that appropriate blinding procedures can be maintained throughout the study duration. [name] and the project manager will train all research personnel (graduate assistants, research assistants, and peer counselors) on the standardized intervention, scripts, protocols for women who need referrals or follow-ups for BF support or maternal well-being, documentation of schedule data collection visits, and establish weekly research team meetings.

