**IFSMT Context variables.**

**Breastfeeding Specific Factors, Physical and Social Environment, Individual and Family Factors and Biomedical Research Informatics**

**Computing System Demographics** The

questionnaires will be used to collect participants' demographics (age, gender, height, weight, race/ethnicity, education, socioeconomic and employment status), BF and medical history (parity, prior BF experience, route of delivery, baseline BNP knowledge, chronic conditions and medication usage), physical and social environment targeting BF support (hospital and home access to professional lactation support, and infant and family characteristics).

**Pain Sensitivity. Pain and Coping.** The Coping Strategies Questionnaire-Revised will assess participants' pain coping strategies (praying, coping self-statement, distancing from the pain, ignoring pain, catastrophizing, and distraction). Participants use a 7-point Likert scale to rate the **frequency** of their use of each coping strategy, "never do that" to "always do that" and its perceived control over their pain. Scores range from 7-42, with higher scores indicating more frequent use of the coping strategy.

**Peripheral and Central Pain Sensitivity.** Peripheral and central sensitivity will be measured using a standardized quantitative sensory testing battery of *cutaneous mechanical pain sensitivity*, involving measures of threshold, ratings of suprathreshold stimuli, temporal summation and after sensations, and pressure pain thresholds using the participant's non-dominant forearm. The testing battery and equipment will match those used by the gold standard German Neuropathic Pain Network. The testing assesses inadequate function (hypoalgesia) as well as gain of function (hyperalgesia) and results are evaluated using age- and gender-matched reference data in pain and control populations. Inter-rater reliability of the *quantitative sensory testing protocol* has been reported in several pain clinical trials, with each individual test demonstrating acceptable correlation coefficients.

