**SA1.** Initially, mixed effects linear modeling will be applied to contrast mean levels of pain at the 1-, 2-, and 3-week time points. The analyses will be repeated for a series of pain outcome measures, including BNP intensity, BNP interference, and cumulative BNP. The models will include “main” effects for intervention and time, an interaction between intervention and time, a random effect for “subject”, and the baseline value of the dependent variable as a covariate. Modeling results will be used to test for a time-by-intervention interaction. If the interaction is non-significant, the model will be re-fitted without it and testing will focus on the main effect of intervention. Regression diagnostics will be applied to all models to identify non-normality in residuals and potentially biasing effects of outlying observations. While mixed effects linear models are resistant to the impact of limited amounts of missing data, we will also utilize multiple imputation methods, as described below, to evaluate the sensitivity of model estimates and testing results to missing observations. Following evaluation of intervention effects at the 1-, 2-, and 3-week time points, we will proceed to assess differences in acute and cumulative BNP intensity and interference at 6, 9, 12, 18 and 24 weeks. Additionally, we will investigate whether subject-level “trends” or “growth curves” in pain levels across all eight study time points differ between the intervention and control conditions. If necessary, demographic variables will be included in the regression models both to account for potential confounding effects that might arise via imperfect randomization and to reduce unexplained between-subject variation in outcome variables.

**SA2. H2A.** We will start by investigating the intervention's effect on proportion of exclusive BF after week 6. Initially, the Pearson Chi-square test will be performed to detect the difference between intervention and control groups at 6, 9, 12, 18, and 24 weeks, respectively. Furthermore, a generalized linear mixed model with a logistic link will be applied to analyze the “main effect” of intervention and time, and “interaction effect” of intervention by time. The procedure to fit and re-fit the model will be similar to the approach for pain measures in SA1. The measure for BF self-efficacy, yield scale scores

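### Recruiting site is in neither the minimisation nor the specified SA1/SA2 models; pre-specifying it is a nearly free gain in precision and credibility

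*Combined protocol and SAP*

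**What the plan says.** **Sources of women.** The screening and design sections name three: UConn Health, the Women's Ambulatory service at Hartford Hospital, and "women receiving private obstetric care at Hartford Hospital, delivering 2900 infants a year with 2320 initiating BF". The sample-size section adds: "We anticipate that approximately 70% of the study sample will be WAHS or HHC patients". Being a patient at one of these places is an inclusion criterion, so the source is known for every participant.

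**Allocation.** Enrollment and Randomization uses Pocock-Simon minimisation, "With 280 expected participants and 6 stratifying characteristics". The factors are listed in full: "Those predictive characteristics include: age, race, breastfeeding experience, expected breastfeeding duration, route of delivery, and intent to return to work". The probability of making the assignment chosen "to minimize imbalance is set to be 90" per cent. Site is not a factor.

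**Models.** In Data Analysis and Management, the SA1 mixed model has intervention, time, their interaction, a random subject effect and the baseline value of the outcome. The SA1 aim also mentions control for prior breastfeeding experience. One optional extension is given: "If necessary, demographic variables will be included in the regression models". The demographics listed under IFSMT Context variables are person-level items and do not include site. SA2 tests exclusive breastfeeding first with unadjusted Pearson chi-square tests at five visits, then with a logistic mixed model built as in SA1. SA3 gives no covariate list.

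**Relevance of site.** Among the context variables, the plan counts "hospital and home access to professional lactation support".

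**The concern.** The three sources differ in setting and probably in case mix, and the plan itself treats access to lactation support as part of the breastfeeding context. If pain or feeding differs by source, that variation has two effects. It widens the standard error of the arm comparison. And if one arm happens to draw more women from one source, the estimate for this particular trial shifts, with no rule fixed in advance for dealing with it. A decision to add site after the randomisation check would be made with the data in view.

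Exclusive breastfeeding is the most exposed outcome. It has no comparable baseline value to adjust for, and its first analysis has no covariates.

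**Working it through.** **Inputs from the plan.** 280 women, 140 per arm; two-sided alpha 0.05; 80% power; d = 0.39; up to 25% loss; about 70% from WAHS or HHC; six factors; best-assignment probability 0.90.

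**Assumptions.** HHC is read as Hartford, so UConn Health supplies about 30%. The split between WAHS and Hartford private is not given. The site difference in outcome, Δ (in SD units, remaining after baseline adjustment), is not given and is varied.

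**1. The plan's own figure.** n per arm = 2(1.960 + 0.842)² / 0.39² = 103.2, so 104. Allowing 25% loss: 104 / 0.75 = 138.7, so 139, against 140 stated. The figure is reproduced. With 140 × 0.75 = 105 per arm, power = Φ(0.39 × √(105/2) − 1.960) = Φ(0.866) = 80.7%.

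**2. Chance site imbalance.** SD of the between-arm difference in Hartford share = √(2 × 0.70 × 0.30 / 140) = 5.5 points.
- Mean absolute gap: 0.798 × 5.48 = 4.4 points; median: 0.6745 × 5.48 = 3.7 points.
- 95% limit: 1.96 × 5.48 = 10.7 points.
- Chance of 10 points or more: 6.8% (normal) or 9.0% (exact hypergeometric, 196 of 280 women from Hartford).
- Among 105 completers per arm: SD 6.3 points, 95% limit 12.4, chance of 10 points or more 11.4%.
- With three sources at assumed splits such as 40/30/30, and plain 1:1 allocation, the chance that at least one source differs by 10 points or more is about 18–20%.

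**3. Does the six-factor minimisation balance site indirectly?** Minimisation was simulated with a 70/30 site mix, assumed factor levels and 1,500 trials per setting.

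| Assumed link between race and site | SD of gap (points) | 95% limit (points) | Chance of 10 or more |
|---|---|---|---|
| None | 5.5 | 11.0 | 7.4% |
| Moderate | 4.8 | 9.3 | 3.5% |
| Strong | 3.6 | 7.1 | 0.3% |

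Indirect balance helps only as far as the balanced factors track site.

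**4. Consequence.** A gap of g shifts the estimate by g × Δ. Site accounts for 0.70 × 0.30 × Δ² = 0.21Δ² of the variance, and adjusted power is Φ(0.39 × √(105/2) / √(1 − 0.21Δ²) − 1.960).

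| Δ (assumed) | Shift, 4-point gap | Shift, 10-point gap | Variance removed | Power with site in model |
|---|---|---|---|---|
| 0.2 SD | 0.008 SD | 0.02 SD | 0.8% | 81.0% |
| 0.3 SD | 0.012 SD | 0.03 SD | 1.9% | 81.4% |
| 0.5 SD | 0.020 SD | 0.05 SD | 5.3% | 82.7% |

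The comparison figures are the design effect of 0.39 and the unadjusted power of 80.7%.

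**The case against.** The strongest reply is that the plan already covers most of this. The baseline value of the outcome absorbs site differences present at entry in the continuous outcomes. Race, expected duration and return to work are balanced, and these may carry much of a clinic-versus-private contrast. Randomisation will be checked descriptively, and demographic covariates, which include education and socioeconomic status, may then be added. All women must have had antenatal breastfeeding basics and a lactation-consultant assessment before discharge, which narrows any difference in hospital support. The intervention is delivered remotely by text and modules.

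Much of this stands, and it is why the effect is small. It does not close the gap. Baseline pain is taken within about 48 hours of birth and cannot carry site differences that arise after discharge. The optional covariates are discretionary and do not name site. The chi-square tests for exclusive breastfeeding have no adjustment.

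A reader might also infer more than the documents support:

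- **That a 10-point imbalance is to be expected.** It is roughly the 95% limit; about 4 points is typical.
- **That the trial is biased or its type I error inflated.** Site was not used in allocation, so its chance variation is already part of the standard error. Omitting it costs precision, not validity.
- **That sensory testing is confounded by examiner or equipment.** Nothing assigns either by site. The plan describes portable equipment, a standardised battery and published inter-rater reliability. Only the follow-up locations are shown to differ.
- **That exclusive breastfeeding differs greatly by site.** The only feeding figures by source are for initiation: 560/700, 800/1,000 and 2,320/2,900, each 80%. They say nothing about later exclusivity, but they give no support for a large gap.
- **That SA3 excludes site.** Its covariates are unspecified and are mentioned only in general terms.

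**Conclusion.** The omission is real: site is known for every woman, is not a minimisation factor and is in no specified SA1 or SA2 model. There is thus no pre-specified correction for a chance imbalance, and site variation beyond baseline remains in the error term.

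The size is modest. If 0.2 to 0.5 SD of site difference survives baseline adjustment, the gain is 0.3 to 2.0 percentage points of power, and an imbalance at about the 95% limit shifts the estimate by at most 0.05 SD. These figures rest on an assumed site effect, a 70/30 mix with HHC read as Hartford, and 105 completers per arm. If the residual site effect is near zero, the gain is near zero too.

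The case for acting is the low cost, the thin reserve (power is set at 80% with 25% loss), and the credibility of having named the covariate before looking at the data.

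**What to change.** - **SA1 and SA2:** pre-specify recruiting site (three levels) as a fixed effect in the linear and logistic mixed models, whatever the randomisation check shows.
- **Exclusive breastfeeding:** name the site-adjusted logistic mixed model as the main result and keep the visit-by-visit chi-square tests as descriptive support.
- **SA3:** include site as a covariate in the exploratory sensory-testing models, because follow-up testing locations differ by site.
- **Allocation:** add site as a seventh minimisation factor only if women remain to be randomised. Recruitment was planned to run through December 2024, so this part may no longer apply; the model change is useful either way.

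The cost is a sentence or two in the analysis section and two degrees of freedom per model, with no new data. If allocation is still open, it also needs one more entry field in the randomisation app.

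### Recruiters see an allocation letter drawn from one shared four-letter code, so unmasking a few women can reveal the arm of every later woman before baseline testing

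*Combined protocol and SAP*

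**What the plan says.** Everything on the mechanics is in the Enrollment and Randomization section of the combined protocol and SAP.

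- **Who runs the draw:** "The resulting R Shiny app will allow the project's recruitment staff to enter the predictive characteristics for a new participant".
- **What they see:** "The blinded group assignment will be presented to the recruitment staff as one of four letters: A, B, C, or D".
- **What happens next:** "That letter will then be entered into REDCap as the new participant's record is set-up".
- **The code:** "REDCap will be programmed to link each of the four letters to a study group", two letters for each arm. "Only the project statisticians, the project manager and the graduate assistant will know the correspondence between letters and group assignments". The section gives the reason for four letters: to make it harder for recruiters to work out the groups.
- **Timing:** "After informed consent and prior to the start of data collection, the participants will be randomized". Baseline sensory testing, samples and questionnaires therefore come after the letter has been shown.
- **Algorithm:** Pocock–Simon minimization on six factors, with probability 0.90 for the assignment that reduces imbalance.

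Elsewhere, the Blinding paragraph says that team members who collect or analyse data are blinded to randomization. Capacity to Consent describes one group of staff at Hartford Hospital as helping with both recruitment and data collection.

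**The concern.** The letter is not a neutral token. It is a label shared by all women who receive it, shown to the people from whom the arm should be hidden. If one woman's arm becomes known, so does the arm of every other woman with that letter. The arms differ in ways a participant can easily describe: Table 1 gives the intervention group a daily log and breastfeeding coaching texts, and gives the control group links to maternal and infant care modules. Women return to clinic at 6 weeks, and recruitment is planned from October 2021 through December 2024, so the code is exposed for a long time.

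What is at stake is mainly the blinding of staff-administered measures. Sensory testing is done at baseline, 6 weeks and 24 weeks, and the baseline round follows randomization. Baseline values of the outcomes are also covariates in the SA1 models.

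A second gap compounds the first. The plan does not say that a draw can be made only once per woman, that calls to the app are logged, or that the draw is tied to an ID.

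**Working it through.** **1. How much must leak to break the code?** The input is four letters, two per arm (Enrollment and Randomization). The number of possible mappings is 4!/(2!·2!) = 6.

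- Learning the arm of one letter leaves 3 mappings.
- A second letter finishes the job if it is in the same arm as the first (1 of those 3 mappings). Otherwise 2 mappings remain.
- A third letter always leaves 1.

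So two or three letters decode all four, and never more than three are needed. If the letters are used evenly (an assumption), each is carried by about 280/4 = 70 women.

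**2. What would a redraw achieve?** This applies only if reruns are possible and the code is known. Assume that the first draw is not recorded and that repeat draws are independent. With chance p of the preferred arm on one draw, one redraw gives 1 − (1 − p)².

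- Tie, p = 0.50: 1 − 0.50² = 0.75.
- Minimization favours the other arm, p = 0.10: 1 − 0.90² = 0.19.

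A recruiter who does not know what the letters mean gains no direction from a rerun.

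**3. Can the next arm be forecast?** Minimization was simulated for 280 women on six factors, using the range measure of imbalance, probability 0.90, and equally likely factor levels. The documents do not give the numbers of levels, so two sets were assumed. The result is the average probability of the more likely arm, given the full history and the new woman's profile.

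| Assumed levels | Minimizing on two arms | Minimizing on four lettered arms |
|---|---|---|
| 2 for every factor | 0.844 | 0.868 |
| 3, 4, 2, 3, 2, 3 | 0.837 | 0.865 |

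That is about 84–87%, against 50% by chance. It requires the code, all past allocations and the factor profiles of earlier women. The code alone reveals the current woman's arm once her letter is shown; it does not forecast the next one.

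**4. What would typing errors cost?** The plan's own figure is reproduced first. For d = 0.39, 80% power and two-sided α = 0.05, n = 2(1.960 + 0.842)²/0.39² gives 104 evaluable per arm. With 25% loss, 104/0.75 gives 139 per arm, or 278 in all, against the stated 280. At 105 evaluable per arm (140 × 0.75), power is 80.7%.

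If a wrong letter is equally likely to be any of the other three, 2/3 of errors change the arm. With m the proportion who change arm, the diluted effect is 0.39 × (1 − 2m). The error rates are assumptions.

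| Error rate | Women changing arm (of 280) | Power |
|---|---|---|
| 0.5% | 0.9 | 80.2% |
| 1% | 1.9 | 79.6% |
| 2% | 3.7 | 78.5% |
| 5% | 9.3 | 75.1% |

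**The case against.** The best defence is that much of the harm would have to be inferred from silence.

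- **Redrawing.** A reader might infer that the letter is drawn before any record exists and can be redrawn at will. The documents do not support that. The section says of the tool: "The interactive tool is developed as an R shiny app embedded in REDCap". Screening data are already held in REDCap, a screening ID exists, and consent precedes the draw. The sentence on entering the letter is passive, so manual keying is a fair reading but is not stated. Reruns may well be blocked or logged. What stands is that the plan does not say so.
- **Forecasting.** A reader might infer that a leaked code makes the next allocation about 85% predictable. It does not, because the forecast also needs the history and profiles, and nothing says that recruiters see these. Since allocation follows consent, selective approach or enrolment would need that full forecast.
- **Typing errors.** Accidental slips are not selective. They cost little power at low rates and face weekly data checks by two staff and three-monthly audits.
- **Existing safeguards.** The sponsor foresaw deciphering, doubled the letters and restricted the key to named roles. Staff follow a script against discussing participant activities. It is not established that the graduate assistant who holds the key also recruits, since the Blinding paragraph names a data management graduate assistant as unblinded.
- **Self-report.** Questionnaires are completed by the women through electronic links, so staff knowledge bears more directly on sensory testing than on the pain scores.

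These replies narrow the point but do not remove it. Doubling the letters raises the number that must be learned to two or three; the letters remain shared and visible to recruiters.

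**Conclusion.** The concern holds in a limited form, and it rests on a stated procedure: recruiters see a shared letter, and one two-letters-per-arm code is described. Learning at most three letters decodes all four. From then on the current woman's arm can be known before her baseline assessments and at later visits, which defeats the blinding that the plan relies on. This assumes that some women's arms become known to staff and that the mapping stays the same. The plan states no change to it, but does not say that it is fixed.

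The missing statement that draws are single-use, logged and tied to an ID is a secondary gap. It matters only together with a broken code, and then moves the chance of a preferred arm from 50% to 75%, or from 10% to 19%, for one redraw. The forecasting range of 84–87% describes a recruiter with full information and assumed factor levels, so it should not be read as the effect of a leaked code. The plan's sample size is reproduced and is unaffected. The procedure should be changed, because a clearly better one is available at little cost.

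**What to change.** 1. Complete and lock the REDCap record (ID, consent, eligibility and the six factors) before the draw.
2. Have the app read the factors from that record and write the allocation once, with a timestamped log of every call, to a field hidden from recruiters and from blinded data collectors.
3. If staff must see a code, make it unique to each participant, so that unmasking one woman says nothing about another.
4. State these controls in Enrollment and Randomization. If some already exist, describing them there closes that part of the point.

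The cost is a small amount of extra programming, by judgement rather than from a figure in the documents, in an interface that the project statisticians are already to create. No sample-size figure changes.
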